2.1. OBJECTIVES

2.1.1. PRIMARY OBJECTIVE:

• To estimate the overall, age and gender specific prevalence of HPV in the oropharynx in patients undergoing tonsillectomy for non-malignant conditions

2.1.2. SECONDARY OBJECTIVES:

- To compare the HPV oropharynx prevalence between different sites—in order to identify the different reservoirs of HPV infection
- To describe the distribution of HPV seropositivity in the study population by age and gender
- To describe HPV-type distribution overall by age, gender, and sampling site
- To describe distribution by age and gender of patients who are both HPV PCR positive and anti-HPV L1 sero-positive – predicting persistent HPV infection
- To provide preliminary estimates of the clearance and persistence of HPV infection and antibodies in the oropharynx, as detected in follow-up oral fluid, finger tips/nail brushings and urine samples
- To assess the presence of anti-L1 HPV antibodies in saliva as a marker of vaccination or previous infection in the oral cavity
- To assess the presence of HPV in the urine
- To assess the presence of HPV in finger tips/nail brushings
- To provide preliminary evaluation of the performance of potential non-invasive tests for the detection of HPV infection in the mouth against HPV detection rates in tonsillectomy and oropharyngeal scrapes
- To identify the change in overall prevalence and distribution of HPV in tonsils over time, and to describe preliminary data on age and gender specific changes over time
- To provide preliminary data on the potential effect of HPV vaccination in the prevention of oral infection

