2.2.2. SECONDARY OUTCOME

- Occurrence of HPV in oral fluid, fingertip/nail brushings, oropharyngeal scrapes and urine samples
- Occurrence of HPV infection clearance in follow-up oral fluid, fingertip/nail brushings and urine samples collected at approximately 3 6 months after the first HPV positive sample
- Occurrence of persistent HPV infection in follow-up oral fluid, fingertip/nail brushings and urine samples collected at approximately 3 6 months after the first HPV positive sample
- Occurrence of HPV infection detected in follow-up oral fluid, fingertip/nail brushings and urine samples collected at approximately 3 6 months after the first HPV negative sample
- Occurrence of anti-HPV L1 antibodies in serum

Occurrence of anti-HPV L1 antibodies in oral fluid sample

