7. STUDY PROCEDURES AND SAMPLE COLLECTION

All samples should be collected in accordance to the study procedure manual developed by GSK with details of sample collection kits, volume of samples to be collected and storage temperature requirements.

For a patient to be eligible for inclusion in the data analysis, the following samples are a minimum requirement:

- Oral samples
- Blood
- Oropharyngeal brushings
- Tonsils

 After written consent is obtained, the patients (above 16 years old only) will complete a short study questionnaire including age, gender, history of tobacco/alcohol use, sexual history including age of start of sexual intercourse, lifetime numbers of sexual partners, engagement in oral sex and lifetime number of oral sex partners etc.

- 2. An HPV vaccination history will also be taken. Consent/assent will also be taken from the patient, parent(s) or their guardian(s), if applicable, to obtain the patient's HPV vaccination status from vaccine and medical health records from their GP and/or other relevant health and educational authorities. The data requested will include confirmation of HPV vaccination status, including dates, number of doses and the type of vaccine given.
- 3. Oral fluid samples will be collected for HPV PCR and HPV antibody tests, using an oral rinse and an exudate collection device respectively.
- 4. A 20 30 ml urine sample will be collected for HPV PCR test.
- 5. Blood serum will be taken for HPV and biomarker serology tests. This can be taken after the patient has been anaesthetised if necessary. 20 mls of blood will be taken from patients aged 16 years and above, 10 mls from patients below 16 years old.
- 6. Once the patient is anaesthetised, two brush cytology scrapings using cytobrushes (provided) will be taken: one from the posterior pharynx including above and below the soft palate so that the adenoidal area is included, and a second separate brush scrape will be taken from the back of the tongue (base of tongue).
- 7. Tonsillectomy will then be performed and the tonsillar tissue will be placed in 10% buffered formalin and sent to the pathology department for paraffin embedding according to a specific protocol.
- 8. Stratified sampling will be employed to ensure that sufficient numbers of patients are recruited from all age groups, especially the age groups between 10 and 20 years old.

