7.4. SAMPLE ANALYSIS

All samples will be analysed using laboratory manuals and standard operating procedures applicable to that organisation.

Table 3: List of laboratories analysing samples

Testing Laboratory	Sample
DDL Diagnostic Laboratory Diagnostic Service Unit [name] The Netherlands	Fresh TonsilsArchive TonsilsOral rinse
Universiteit van Antwerpen Vaxinfectio – CEV [name] [name] Belgium	• Urine
CEVAC Center For Vaccinology UZ GENT - 1BA [name] Belgique	• Serum
InHANSE Laboratory CRC Building School of Cancer Sciences, 3rd Floor, University of Birmingham [name], UK	Nail BrushingsWhite Blood CellsSerum

Testing Laboratory	Sample
GlaxoSmithKline Vaccines Clinical Immunology R & D Department/Building 7 [name] [name] – Belgium	 Oral Mucosal Transudate Urine Fresh Tonsils Archive Tonsils Oropharyngeal brushings

- The oral fluid, nail brushings, oropharyngeal scrapes and urine samples will be tested for HPV DNA by PCR. We may also test them for HPV viral load, viral RNA and p16 RNA. They may also undergo other detection methods, such as in-situ hybridisation (ISH). The oral fluid may also be tested for anti HPV L1 antibodies. Other antibodies e.g. anti E6/7, nucleic acids, other HPV related proteins and total antibodies may also be assayed.
- 2. The tonsil samples will be tested for HPV DNA by PCR. They may also undergo other forms of detection of HPV such as in-situ hybridisation and other tests that may be developed in future for HPV detection. The tonsil samples will also be examined histologically for pre-malignancy to examine the molecular profile and genetic changes within the pre-malignant sample and to compare it to those of the normal tonsil, using immunohistochemical, DNA, mRNA and proteomics techniques.
- 3. The blood samples will be tested for antibodies to the HPV L1, and other HPV antibodies. Also other protein testing may be performed. Samples may undergo other forms of detection for HPV within the blood, such as HPV nucleic acids and HPV virus particles.

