12.2. ANALYSIS OF OUTCOME MEASURE

The statistical analyses will be described in detail in a statistical analysis plan (SAP). All of the tests will be two-sided with an alpha level of 0.05.

12.2.1. PRIMARY OUTCOME:

The overall prevalence will be estimated as the number of patients with HPV detected in tonsils divided by the total number of patients with available samples. An exact 95% confidence interval will be computed. The prevalence per age and gender group will be calculated similarly.

The relationship between prevalence and age will be explored using logistic regression with the age as a continuous covariate and gender and centre as categorical covariate. The number of degrees (one, two, three) of the model and possible variable transformation (e.g. log-transformation of age) could be determine based on graphical analysis of prevalence versus age relationship and on model fit criteria (e.g. AIC).

12.2.2. SECONDARY OUTCOME:

The overall prevalence will be estimated as the number of patients with HPV detected in oral fluid, oropharyngeal scrapes and urine samples divided by the total number of patients with available samples. An exact 95% confidence interval will be computed.

The prevalence per age and gender group will be calculated similarly. Prevalence rate will be compared among centres using a Cochran-Mantel-Haenszel test with stratification by age group.

Relationship between the prevalence of HPV in tonsils and the prevalence of HPV in oropharyngeal scrapes, oral fluid, and urine samples will be analysed by computing kappa coefficient. Specificity, sensitivity, positive predictive value and negative predictive value of HPV detection in the different sample types will be derived using the oral sample results as the reference.

Relationship between presence of anti-HPV L1 antibody in oral fluid samples and occurrence of HPV in tonsils and/or in oropharyngeal scrape samples will be analysed by computing kappa coefficiency. Specificity, sensitivity, positive predictive value and negative predictive value of anti-HPV L1 antibody assay will be derived using the oral sample results as the reference.

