The rate of HPV persistence will be calculated as the proportion of baseline HPV-positive patients who again test HPV-positive in oral fluid, fingertip/nail brushings and urine samples collected after approximately 3 - 6 months. The rate of oral HPV infection clearance will be calculated as the proportion of baseline HPV-positive patients who test HPV-negative in oral fluid, fingertip/nail brushings and urine samples collected after approximately 3 - 6 months.

HPV incidence will be calculated as the proportion of baseline HPV-negative patients who test HPV positive in oral fluid, fingertip/nail brushings and urine samples collected after approximately 3 - 6 months. Exact 95% confidence intervals will be computed.

Multi variable regression models will be used to calculate the odds ratios of different risk factors for having HPV DNA in the tonsil and in the oropharynx, Variables to be included in the model (e.g. serological markers and clinical risk factors such as HPV vaccination status, tobacco and alcohol use) will be selected on the basis of descriptive statistics/possible causal relationship and/or a stepwise approach. Analysis of results may be performed to identify a possible marker or combination of markers for screening for persistent HPV infections in the oropharynx.

Among females in the target age class for vaccination (12 to 24 years), exploratory analyses will compare the HPV prevalence rate in HPV vaccinated and non HPV vaccinated patients using a Fisher's exact test. Association between HPV vaccine and oral HPV infection will be assessed using a case-control approach. Cases will be patients with HPV positive oral sample and controls will be patients with HPV negative oral sample. The exposure to vaccine will be compared between the case and the control groups using logistic regression, OR and its 95% confidence interval will be derived.

Prevalence of HPV in tonsils will be described and compared between the current cohort and the comparison historical cohort using a Cochran-Mantel-Haenszel test with stratification by age group and gender.

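### Section 12.2.2 judges oral-fluid anti-L1 only against current HPV detection, which leaves the objective on vaccination or previous infection without an analysis

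*Protocol*

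**What the plan says.** The objective in protocol section 2.1.2 reads "To assess the presence of anti-L1 HPV antibodies in saliva as a marker of vaccination or previous infection in the oral cavity". The target condition is therefore vaccination or an infection in the past.

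Section 12.2.2 names two analyses of the assay:

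- The kappa analysis concerns the "Relationship between presence of anti-HPV L1 antibody in oral fluid samples and occurrence of HPV in tonsils", in oropharyngeal scrapes, or in both.
- For accuracy, sensitivity and specificity, together with "positive predictive value and negative predictive value of anti-HPV L1 antibody assay will be derived using the oral sample results as the reference".

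The protocol does not define the oral sample results. Later in the same section the term denotes an HPV-positive or HPV-negative result: "Cases will be patients with HPV positive oral sample".

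Two comparators closer to the objective are already planned. Section 2.2.2 lists "Occurrence of anti-HPV L1 antibodies in serum" as an outcome, and section 7.4 states "The blood samples will be tested for antibodies to the HPV L1, and other HPV antibodies". Section 7 says "For a patient to be eligible for inclusion in the data analysis, the following samples are a minimum requirement", and its list contains both oral samples and blood. Section 7 also provides for obtaining HPV vaccination status, dates, doses and vaccine type from records. Section 12.2.2 uses serological markers only as possible covariates in a model for HPV DNA. It uses vaccination as a covariate there and as the exposure in analyses of HPV detection. Neither is set against oral-fluid anti-L1.

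**The concern.** Antibody can reflect an infection that is over, or a vaccine, while a PCR result reflects virus present on the day of sampling. When PCR is the reference, two groups that the objective wants the marker to identify are scored as errors: vaccinated patients without current HPV, and unvaccinated patients who have cleared an infection. Setting vaccinated patients aside removes only the first group.

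At stake is whether a stated secondary objective gets an answer. Kappa, specificity and PPV from section 12.2.2 would mix the quality of the assay with the proportion of patients who have antibody for reasons other than current infection. They could not be read as evidence for or against its value as a marker of vaccination or past infection. The primary prevalence estimate is not affected.

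**Working it through.** The protocol gives no figure for this assay, so there is nothing to reproduce. The check scores a marker that is perfect for the objective against current HPV DNA.

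**Inputs from the protocol**

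- Cohort 925 (section 12.3).
- 150 HPV-vaccinated women (section 12.4).
- HPV prevalence about 6.5% (section 12.3).
- Pooled tonsil rate from Table 2 in section 1.4: (2+0+3+1+5+6+13+0+0) / (195+226+69+50+64+106+206+48+14) = 30/978 = 3.1%, taken as 3%.

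**Assumptions not in the protocol**

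- Every DNA-positive patient is antibody-positive.
- Vaccinated patients are DNA-negative.
- The share of patients with past infection is as given in each case below.

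**Formulas.** Let d be the DNA-positive proportion and m the antibody-positive proportion, with all DNA positives inside m. Then:

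- sensitivity = 1 and NPV = 1
- specificity = (1−m)/(1−d)
- PPV = d/m
- observed agreement Po = 1−(m−d)
- chance agreement Pe = dm + (1−d)(1−m)
- kappa = (Po−Pe)/(1−Pe)

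**Case 1: whole cohort, no cleared infections**

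- Vaccinated share = 150/925 = 0.162, so m = 0.065 + 0.162 = 0.227.
- Specificity = 0.773/0.935 = 83%. PPV = 0.065/0.227 = 29%.
- Po = 1 − 0.162 = 0.838. Pe = 0.065×0.227 + 0.935×0.773 = 0.737.
- Kappa = (0.838−0.737)/(1−0.737) = 0.38 (unrounded inputs).

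If 10% or 20% of the remaining patients had cleared an infection, kappa would be 0.27 or 0.20 and PPV 21% or 17%. With no cleared infections, kappa is 0.17 at 2% DNA prevalence and 0.48 at 10%. Table 7 uses 1100 patients, which equals 1250 − 150. If the 150 is therefore set against 1250 rather than 925, kappa at 6.5% is 0.47.

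**Case 2: unvaccinated patients only.** Here m = e, the share ever infected, assumed to be 10% to 25%.

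| d | e | Specificity | PPV | Po | Pe | Kappa |
|---|---|---|---|---|---|---|
| 3% | 10% | 93% | 30% | 0.930 | 0.876 | 0.44 |
| 3% | 25% | 77% | 12% | 0.780 | 0.735 | 0.17 |
| 6.5% | 10% | 96% | 65% | 0.965 | 0.848 | 0.77 |
| 6.5% | 25% | 80% | 26% | 0.815 | 0.7175 | 0.35 |

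The marker makes no error in any row. The spread in kappa comes entirely from the gap between current and past infection.

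**Reading of the reference.** If the oral sample results mean HPV detection, the reference is current infection. If they meant the oral-fluid antibody result, the comparison would be circular. On neither reading are they serum anti-L1 or vaccination status.

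**The case against.** The strongest defence is that section 2.1.2 has another objective: a preliminary evaluation of non-invasive tests for detecting HPV infection, judged against tonsil and scrape results. The antibody analysis names those same specimens. For that question current HPV is the right reference, and low specificity would be a correct answer. This stands, and the DNA comparison should keep its place as a performance analysis. It does not supply an analysis for the marker objective.

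Other points that stand in part:

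- **Past-infection share.** It is assumed. At 6.5% DNA and 10% ever infected, kappa is 0.77, which is not poor, and sensitivity and NPV are 100% throughout. Case 1 needs no past-infection share, but it does rest on the 150 vaccinated and on their being DNA-negative.
- **Descriptive reading.** The objective could mean simply reporting how often the antibody is present, and its occurrence in oral fluid is a listed outcome. That covers presence but not value as a marker.
- **Testing is optional.** Section 7.4 says only that oral fluid may be tested for anti-L1, so paired results are not assured.
- **The SAP could add the comparison.** This is true, and the absence is established for the protocol only. But the protocol does fix a reference for this assay, and a SAP that merely follows it would inherit the mismatch.

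A reader might infer that a useful test would be wrongly discarded. The documents do not support that, since there is no threshold or decision rule for the assay. A reader might also infer that a perfect oral marker would score 100% against serum. That does not follow either: the objective concerns the oral cavity, whereas serum antibody can come from infection at any site.

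**Conclusion.** The point holds for the protocol as written. Section 12.2.2 fixes current HPV detection as the only reference for oral-fluid anti-L1, and that reference cannot answer the objective on vaccination or previous infection. For a perfect marker, kappa is about 0.38 and PPV about 29% with 150 of 925 vaccinated, 6.5% DNA prevalence, vaccinated patients DNA-negative, all DNA positives antibody-positive and no cleared infections. In unvaccinated patients kappa lies between 0.17 and 0.77 for DNA prevalence of 3% or 6.5% and an assumed ever-infected share of 10% to 25%. Only kappa, specificity and PPV are affected; sensitivity stays at 100% under these assumptions. This is a secondary objective, and the change should be made because the comparators are already planned.

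**What to change.** In section 12.2.2, keep the comparison with HPV DNA. Define the oral sample results, state that the reference is current infection, and name the objective it serves, which is the one on non-invasive tests for detecting HPV.

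For patients whose oral fluid is assayed for anti-L1, add:

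- (a) oral-fluid anti-L1 positivity by documented vaccination status, with exact 95% confidence intervals;
- (b) among unvaccinated patients, agreement of oral-fluid with paired serum anti-L1: kappa, and positive and negative percent agreement with exact 95% confidence intervals. State that serum reflects infection at any site and is an imperfect reference for oral infection.

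The cost is a short wording change and two more tables, with no new specimens or records. The remaining weakness is the imperfect serum reference, which is why (b) should be reported as agreement and not as accuracy. If the SAP already contains these tables, only the protocol wording needs aligning.

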12.3. SAMPLE SIZE CONSIDERATIONS

An analysis of current literature suggests that in a population recruited between 1990 and 2000, the prevalence of oral HPV was about 6.5%, varying from 0% - 10%. However, in an analysis of oropharyngeal scrapes and oral washings, the prevalence of HPV detection was much higher at 31%.

Pilot data of patients having tonsillectomy at University Hospital Coventry over two 3-month time periods are shown below in table 3. The number of tonsillectomy operations performed at the Heart of England NHS Foundation Trust - is approximately 50% of that for University Hospital Coventry quoted below.

Table 5: The number of tonsillectomy operations performed at University Hospital Coventry.

Age Group*	Number of Monthly recruitment (%)		
0-4	7 (12%)		
5-9	12 (20%)		
10-14	7 (12%)		
15-19	10 (17%)		
20-24	6 (10%)		
25-29	5 (8%		
30-34	4 (7%)		
35-39	5 (8%)		
40-44	1 (2%)		
45-49	1 (2%)		
50-69	1 (2%)		
Total	59		

^{*}There was an equal distribution of males and females in the group.

We plan to enrol 925 patients. The precision of the overall prevalence estimate that would be achieved with such a number is summarised in Figure 1 for prevalence ranging from 1 to 31 %. For example, if the observed prevalence is 10 %, the 95 % confidence interval for the overall population will be 8.4 to 11.8 % corresponding to a relative precision of 17 %.

[figure not shown]

Figure 1: Precision (95% confidence interval) of the prevalence estimate versus the prevalence observed in a random sample of 1250 patients.

We will also undertake a stratified sampling strategy to allow comparisons between those aged 14 and under (non-exposed, approximately one third of the cohort), and patients over 14 years of age (exposed) to allow the determination of the age of acquisition of infection and the optimal age of start of vaccination. The stratified sampling strategy will recruit patient subgroups as follows:

Table 6: The stratified sampling strategy for patient recruitment.

Age group	Sample size (%)		
0-4	150 (16.5%)		
5-9	150 (16.5%)		
10-14	150 (16.5%)		
15-19	150 (16.5%)		
20-24	150 (16.5%)		
25-34	100 (11%)		
35-44	60 (5.5%)		
45-65	15 (1.0%)		
Total	925		

[figure not shown]

Figure 2: Precision (95% confidence interval) of the prevalence estimate versus the prevalence observed in a random sample of 100, 150, and 250 patients.

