12.4. POWER CALCULATIONS

For the historical comparison analysis, assuming a two-sided test, 0.05 alpha level, baseline prevalence of 2 to 8%, and exclusion of 150 HPV vaccinated women from the analysis, we would have approximately 80% power to detect an absolute increase in overall HPV prevalence of at least 2 to 4% (see table below). Exploratory analyses of changes in HPV prevalence by gender and age and by vaccination status will be descriptive.

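### The kappa and accuracy analyses of oral-fluid anti-L1 antibody do not separate vaccinated patients, which lowers specificity, PPV and kappa by an amount the protocol does not allow one to fix

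*Protocol*

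**What the plan says.** Section 12.2.2 of the protocol fixes two analyses of the antibody in oral fluid. The first is a kappa coefficient for the "Relationship between presence of anti-HPV L1 antibody in oral fluid samples and occurrence of HPV in tonsils and/or in oropharyngeal scrape samples". The second is a set of accuracy measures: sensitivity and specificity, and also "positive predictive value and negative predictive value of anti-HPV L1 antibody assay will be derived using the oral sample results as the reference". Neither sentence names an analysis population or mentions vaccination.

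The matching objective in section 2.1.2 is "To assess the presence of anti-L1 HPV antibodies in saliva as a marker of vaccination or previous infection in the oral cavity". Two further objectives in that section use serology: seropositivity by age and gender, and the distribution of "patients who are both HPV PCR positive and anti-HPV L1 sero-positive".

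Vaccination is taken into account elsewhere:
- Section 12.4 assumes "exclusion of 150 HPV vaccinated women from the analysis" for the historical comparison.
- Section 12.2.2 compares vaccinated with unvaccinated females aged 12 to 24, and lists vaccination status as a candidate covariate in the risk-factor models.
- Section 7 takes a vaccination history and, with consent or assent, seeks records: "The data requested will include confirmation of HPV vaccination status, including dates, number of doses and the type of vaccine given".

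**The concern.** The reference in both analyses is current HPV detection (the oral sample result is read here as its HPV DNA result). By the protocol's own objective, the index test also responds to vaccination. A vaccinated patient without HPV who carries vaccine antibody is therefore a correct finding under section 2.1.2 and an error of the assay under section 12.2.2.

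Two questions are merged: whether the antibody tracks HPV in the mouth, and whether it reveals vaccination. Pooled figures could understate the first because of the second. They would also depend on how many vaccinated patients happened to be recruited, so they would not carry over to a population with different vaccine uptake. Unsplit tables of seropositivity by age and gender have the same mixture in the vaccinated age and sex groups.

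**Working it through.** The protocol states no expected kappa, sensitivity, specificity or predictive value for this assay, so there is no figure to reproduce. The check is an expected 2×2 table that pools vaccinated and unvaccinated patients.

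**Inputs from the protocol**
- Enrolment N = 925 (section 12.3: "We plan to enrol 925 patients").
- Vaccinated patients: 150 (section 12.4), so 150/925 = 16.2%.
- The 150 may belong to a larger target: Table 7 uses 1100 per cohort, 1100 + 150 = 1250, and the caption of Figure 1 still refers to 1250. The alternative share is 150/1250 = 12.0%.
- HPV prevalence p: 6.5% as the central value and 10% and 31% as higher values (section 12.3); 2% is the lowest baseline in section 12.4.

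**Assumptions**
- v, the proportion of vaccinated patients with anti-L1 in oral fluid, is not in the protocol. It is varied from 10% to 95%.
- The assay is otherwise perfect: every infected patient is positive and every uninfected unvaccinated patient is negative.
- Prevalence is the same in vaccinated and unvaccinated patients. If vaccination lowers infection, vaccinated patients add more false positives and fewer true positives.

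**Formulas**
- Infected, all true positives: D = N·p
- False positives: FP = 150·(1 − p)·v
- True negatives: TN = N − D − FP
- Specificity = TN/(N − D) = 1 − (150/N)·v
- PPV = D/(D + FP)
- Kappa = (po − pe)/(1 − pe), with po = (D + TN)/N and pe = [(D + FP)·D + TN·(N − D)]/N²

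**Worked case, N = 925, p = 6.5%, v = 95%**
- D = 925 × 0.065 = 60.1; uninfected = 864.9
- FP = 150 × 0.935 × 0.95 = 133.2; TN = 731.6
- Specificity = 731.6/864.9 = 0.85
- PPV = 60.1/193.4 = 0.31
- po = 791.8/925 = 0.856; pe = 0.753; kappa = 0.103/0.247 = 0.42

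**Range over v, N = 925, p = 6.5%**

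| v | Specificity | PPV | Kappa |
|---|---|---|---|
| 10% | 0.98 | 0.81 | 0.89 |
| 30% | 0.95 | 0.59 | 0.72 |
| 60% | 0.90 | 0.42 | 0.55 |
| 95% | 0.85 | 0.31 | 0.42 |

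In unvaccinated patients alone, all three would be 1.00.

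**Range over prevalence, N = 925, v from 10% to 95%**

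| p | PPV | Kappa |
|---|---|---|
| 2% | 0.56 to 0.12 | 0.71 to 0.18 |
| 10% | 0.87 to 0.42 | 0.92 to 0.52 |
| 31% | 0.97 to 0.75 | 0.97 to 0.77 |

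Specificity does not depend on p.

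**Smaller vaccinated share, 150 of 1250, p = 6.5%, v = 95%:** specificity 0.89, PPV 0.38, kappa 0.50.

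**Imperfect assay (assumed sensitivity 0.60 and specificity 0.95 in the unvaccinated), p = 6.5%, 150 of 925**

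| Population | Specificity | PPV | Kappa |
|---|---|---|---|
| Unvaccinated only | 0.95 | 0.455 | 0.48 |
| Pooled, v = 30% | 0.91 | 0.315 | 0.36 |
| Pooled, v = 95% | 0.80 | 0.19 | 0.21 |

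At v = 95%, taking vaccinated infected patients to be antibody positive at the same 95% rate, pooled sensitivity is 0.66 and NPV about 0.97. Neither falls materially.

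**The case against.** The best defence is that the protocol is silent on this point and not explicit. It refers the details of analysis to a SAP that is not at hand, and a split of a secondary table by vaccination status could be added there. That is true. But section 12.2.2 already names the statistics, the comparator and the reference, and nothing in the protocol calls for the split. The wording as it stands leads to pooled figures.

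A reader might infer that the assay is bound to look poor. The documents do not support that. With every vaccinated patient antibody positive and 150 of 925 vaccinated, specificity would be 83.8%, PPV 30% and kappa 0.40 at 6.5% prevalence, but this is a worst case. It needs a 100% antibody rate in oral fluid, which the protocol nowhere states. It also divides an allowance made for a different analysis, and apparently for a target of 1250, by 925. At v between 10% and 30%, kappa stays at 0.72 to 0.89.

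A reader might also infer that seropositivity by age and gender would chiefly reflect the girls' vaccination programme. The protocol gives no infection-related seroprevalence to compare with, and its vaccination target class is females aged 12 to 24, so any mixing is concentrated in a few cells. Nor is serious contamination of the group that is both PCR positive and seropositive shown: at 6.5% prevalence only about 150 × 0.065 ≈ 10 vaccinated patients could enter it.

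Finally, restriction is not a complete cure. Section 2.1.2 also calls the antibody a marker of previous infection, so antibody left by a cleared infection will still disagree with current HPV DNA in unvaccinated patients. That objection stands.

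**Conclusion.** The point holds as a downward bias of uncertain size. As written, section 12.2.2 scores vaccine antibody in HPV-negative patients as assay error, against the protocol's own description of the antibody. Specificity, PPV and kappa fall whenever vaccinated patients carry more antibody than unvaccinated ones. At the prevalences up to 10% considered in the protocol, the loss ranges from slight to large, with PPV and kappa much more exposed than specificity; at 31% it is smaller.

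The figures rest on an assumed antibody rate after vaccination, a vaccinated share of 12% to 16%, and equal HPV prevalence in the two groups. The analysis is secondary, with no decision threshold attached, and the primary prevalence estimate is untouched. The change is still worth making because it uses data the study already seeks.

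**What to change.** In section 12.2.2, or in the SAP with a reference to that section:
- Report kappa, sensitivity, specificity, PPV and NPV of anti-L1 in unvaccinated patients as the main result, and show vaccinated patients separately.
- Present seropositivity by age and gender split by vaccination status.
- State how patients with unconfirmed vaccination status are classified, since record retrieval depends on consent or assent.
- Acknowledge that antibody from cleared past infection still counts as false positive against current HPV DNA.

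The cost is wording only, since vaccination history is already on the Baseline Form (section 9.1, Table 4). The main accuracy analysis loses about 150 patients, leaving about 925 − 150 = 775 and slightly wider confidence intervals.
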